11.3.3 Case Record Form (CRF)	19
11.3.4 Archive and data retention.....	19
11.3.5 Audit and inspection.....	19
12 Ethical and Regulatory Requirements	20
12.1 Ethics Committee	20
12.2 Informed consent	20
12.3 Subject confidentiality.....	21
12.4 Revision of the study proposal	21
12.5 Proposal deviation.....	21
13 Publication Policies.....	21
14 Devices.....	22
14.1 Count of research-related devices	22
14.2 Return of research-related devices	22

Proposal No.: C-BSEAL-001

Date of proposal: V1.0/2019-11-18

14.3 Complaint about devices	22
14.3.1 Complaint about devices	22
References	23
Table 1: Product Specifications and Models.....	6

Summary of the Proposal

Research Topic:	A Multi-center, Retrospective Registry Study on the Safety of Bactiseal Catheterization
Research Purpose:	This study aimed to continue to evaluate safety information from subjects implanted with a catheter (trade name: Bactiseal) produced by Codman & Shurtleff, Inc. of the United States. Device safety would be assessed based on all the adverse events that occurred within one year after the subjects implanted the catheter.
No. of Subjects:	50
No. of Research Centers:	3 research centers
Research Design:	
This study was designed to be single arm, multi-center, and retrospective.
 
A total of 50 patients would be retrospectively enrolled. Information would be collected on adverse events of subjects enrolled within one year after the implantation of the Bactiseal Catheter from August 07, 2018 to January 31, 2021.
 
The following information would be collected from subjects' medical records or hospitals' databases (if any):
 
 1. General condition of the subjects 2. Intraoperative condition and catheter implantation 3. Information on the shunt product 4. Adverse events of subjects within one year after the operation and classification of the adverse events 5. Relevant examinations in case of postoperative infection 6. Other adverse event-related information (except anticipated adverse events)
Research Duration:	2020-
Inclusion Criteria:	
Subjects who met all of the following inclusion criteria would be enrolled:
 
 1. The informed consent was exempted by the Ethics Committee of a research center. Either a subject or his/her legal representative signed the informed consent form (ICF) prior to enrollment. 2. A subject had an indication suitable to use Bactiseal Catheter. 3. A subject received a hydrocephalus shunt at least one year ago.
Exclusion Criteria:	Subjects who met any of the following exclusion criterion were excluded:

	
1. A subject didn't have an indication suitable to use the product.2. A subject was known to be allergic to a component or ingredient of the product to be implanted, including silicone tubing, rifampicin, and clindamycin.3. According to the comprehensive judgment of an investigator, a subject had an infection of the implant site when the shunt was implanted, such as ventriculitis, meningitis, peritonitis, and local implant skin infection.4. A subject was simultaneously implanted with another shunt system different from Bactiseal Catheter.5. A subject had a contraindication of the shunt operation.6. A subject had uncorrected coagulopathy or any bleeding disorder.
Endpoint	
1. Non-infection rate of a subject within one year2. Type and incidence of adverse events of a subject within one year

Time and Data Collection Form

	Screening	Preoperative	Operation	Postoperative follow-up
Time of data collection	NA	-30 to -1 days	0	Days 1-365
Signed the ICF (if applicable) ¹	X			
Review of inclusion and exclusion criteria	X			
Medical History		X		
Laboratory examination		X		X+
Operative process			X	
Device application record			X	
Adverse events ²			X*	X*
Serious Adverse Events			X*	X*
End of study/exit			X	X
Record of concomitant medication ³		X*	X*	X*
Record of concomitant treatment ⁴			X*	X*

+	Suspicious or proven infection
*	If any

Notes: 1. The ICF (if applicable) needed to be completed before screening.

2. A postoperative anticipated adverse event was not counted as an adverse event.

3. Only antibiotics and medications related to postoperative adverse events were recorded. Only the administration of antibiotics within seven days prior to the operation was recorded.

4. Only the treatment and operation associated with postoperative adverse events were recorded.

Abbreviations:

AE	Adverse events
CRF	Case Record Form
CV	Curriculum Vitae
EC	Ethics Committee
ICF	Informed Consent Form
IFU	Instructions for Use
GCP	Good Clinical Practice
NMPA	National Medical Products Administration
SAE	Serious adverse event
SDV	Source data verification
UADE	Unanticipated adverse device effect

1 Introduction

1.1 Background and principle

Abnormal enlargement of part or all of subarachnoid space or ventricles, the abnormal accumulation of cerebrospinal fluid (CSF) in subarachnoid space or ventricles is called hydrocephalus. It is a circulation disorder of CSF caused by many pathological reasons¹. A shunt system mainly drains CSF from the accumulation site to the abdominal cavity, the lumbar cistern, and the atria through a catheter so as to address dilated ventricles and alleviate the pressure on the brain.

The earliest permanent CSF shunt operation occurred in 1893. A glass catheter was placed in a lateral ventricle of a patient with hydrocephalus, the end of which was placed under the skin. The head circumference of the patient was significantly reduced after the operation². The principle of modern shunt operation can be dated back to the 1870s. Ventriculoperitoneal shunt operation had become a common treatment for hydrocephalus³. China released *Specialist Consensus on the Standardized Treatment of Hydrocephalus in China* in 2013, which regarded CSF shunt as an important operation for hydrocephalus and proposed suggestions on technical key points.

However, in terms of the treatment of neurosurgical diseases, the incidence of complications of shunt operations is the highest, mainly including shunt infection, obstruction or rupture of a shunt catheter, displacement of an intracranial or abdominal shunt catheter, excessive or insufficient drainage of CSF, intracranial hemorrhage, and epilepsy¹. Infection is a common complication and important cause of revision. Its incidence rate is 3-29%. Approximately 90% of the cases occur within one year after the operation. If it is combined with ventriculitis, the mortality rate can be as high as 30-40%³. For children, even if the infection can be controlled, long-term complications, such as epilepsy, cognitive impairment, and physical and delayed psychological development, may occur⁴.

From previous analysis of literatures, among a total of 8,588 shunt operations (3,291 cases with an antibiotic-impregnated catheter, 5,297 cases with a non-antibiotic-impregnated catheter), the postoperative infection of an antibiotic-impregnated catheter was 3.6%, while that of a non-antibiotic-impregnated catheter was 7.2%⁵. From most recent publication⁶, (need to put reference here), 1605 cases were randomized to receive either a standard shunt (n=536), an antibiotic-impregnated shunt (n=538), or a silver shunt (n=531). Of those, 1594 had a shunt inserted without evidence of infection at the time of insertion (533 in the standard shunt group, 535 in the antibiotic shunt group, and 526 in the silver shunt group). The subjects were followed up for a median of 22 months (IQR 10~24; 53 withdrew from follow-up). 32 (6%) of 533 evaluable patients in the standard shunt group had a shunt revision for infection, compared with 12 (2%) of 535 evaluable patients in the antibiotic shunt group. The combined postoperative infection of an antibiotic-impregnated catheter was 3.2%, while that of a non-antibiotic-impregnated catheter was 7.1%.

In addition to infection, complications of CSF shunt operations include excessive and insufficient drainage of CSF associated with pressure regulation; obstruction of the shunt catheter, usually due to a poor position of an intracranial shunt catheter, the accumulation of red blood cells or brain tissues in the shunt pump, or wrapping of a shunt catheter by abdominal omentum majus; rupture of shunt catheter, mostly occurring at the junction of the catheter and the pump and a subcutaneous area; and rare complications, such as displacement of a shunt catheter, wound, intracranial hemorrhage, and symptoms of Parkinson's Disease¹.

Bactiseal Catheter manufactured by Codman & Shurtleff, Inc. in the United States is a silicon catheter impregnated in rifampicin and clindamycin. Thanks to the slow release of the two antibiotics on the surface of the catheter, the colonization of Gram-positive bacteria on the catheter is reduced. Meta analysis⁷ demonstrated that Bactiseal can significantly reduce the infection rate after shunting.

Meanwhile, Bactiseal has been safely used around the world for more than a decade. However, there is a lack of data on the safety of the product in long-term follow-up and clinical application in the Chinese population.

1.2 Research-related devices

Devices verified in this study were catheters (trade name: Bactiseal) manufactured by Codman & Shurtleff, Inc., U.S.A. Its registration number is G.J20183132246. Please refer to the table below for the product specifications and models in this study.

Table 1: Product Specifications and Models

Model	Description	Inner diameter (mm)	Outer diameter (mm)
823072	Ventricle and abdominal catheter	1.4/1.0	2.7/2.2
823073	Ventricle catheter	1.4	2.7
823074	Abdominal catheter	1.0	2.2

2. Benefits/Risks

2.1 Benefits

Bactiseal Catheter serves as a component of the shunt system of hydrocephalus treatment. Hydrocephalus shunt operations can alleviate or eliminate hydrocephalus and improve clinical symptoms and signs. Meanwhile, retrospective collection of data and experience of clinical safety can be used as a reference for investigators and enterprises and conducive to the diagnosis and treatment of future subjects. However, such data and experience had no extra benefits for the participants in this study.

2.2 Risks

This is a retrospective study. It did not intervene in subjects' normal treatment. It objectively collected patients' clinical data. Hence, there were no additional risks associated with participating in this study.

3 Research purpose

3.1 Indications

Bactiseal Catheter: Bactiseal Catheter serves as a component of the shunt system of hydrocephalus treatment.

3.2 Purpose

This study aimed to collect safety information from subjects implanted with a catheter (trade name: Bactiseal) produced by Codman & Shurtleff, Inc. of the United States. Device safety would be assessed based on all the adverse events that occurred within one year after the subjects were implanted with the catheter.

4. Research Design

This study was designed to be single arm, multi-center, and retrospective.

This is continued access study to enroll additional 50 new subjects, with total combined 150 subjects. The historical study is DPS-201501.

It would collect information on adverse events of subjects enrolled within one year after the implantation of Bactiseal Catheter from August 07, 2018 to August 31, 2019, through case review or hospital database (if any).

The following information would be collected from subjects' medical records:

1. General condition of the subjects
2. Intraoperative condition and catheter implantation
3. Information on the shunt product
4. Adverse events of subjects within one year after the operation and classification of the adverse events
5. Relevant examinations in case of postoperative infection
6. Other adverse event-related information (except anticipated adverse events)

Information on adverse events would be collected. And the safety of clinical application of the product would be assessed.

5. Endpoint

5.1 Endpoint

1. Non-infection rate of a subject within one year
2. Type and incidence of adverse events within one year of a subject

5.2 Safety indicators

The incidence of adverse events was observed in line with the IFU. Key attention should be paid to:

- Obstruction of a cerebral ventricular catheter
- Falling of a catheter
- Poor position of a catheter
- Intestinal perforation, abdominal and pseudocysts, umbilical fistula, pseudo-acute appendicitis, infection, and ascites
- Subcutaneous twist, rupture, distal obstruction, and distal retraction from the abdominal cavity
- Failure of a shunt catheter

- Mechanical failure

- Obstruction or infection of the shunt path

- Leakage of CSF in an implanted shunt catheter

- Excessive drainage

- Damage of intracranial or abdominal tissue

- Fibrous adhesion

6 Study Population

6.1 Selection of subjects

Subjects who received a hydrocephalus shunt operation between August 07, 2018 to August 31, 2019 and met the inclusion criteria were enrolled. As this was a retrospective study, it would apply for the exemption of informed consent from the Ethics Committee of a center. For the centers which did not exempt informed consent, the informed consent process would be completed prior to the start of data collection, either by telephone or by anyway approved by the Ethics Committees.

6.2 Inclusion criteria

Subjects who met all of the following inclusion criteria would be enrolled:

1. The informed consent was exempted by the Ethics Committee of a research center. Or a subject or his/her legal representative signed the informed consent form (ICF) prior to the enrollment;
2. A subject had an indication suitable to use Bactiseal Catheter;
3. A subject received hydrocephalus shunt at least one year ago.

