6.3 Exclusion criteria

Subjects who met any of the following exclusion criterion were excluded:

1. A subject didn't have an indication suitable to use the product;
2. A subject was known to be allergic to a component or ingredient of the product to be implanted, including silicone tubing, rifampicin, and clindamycin;
3. According to the comprehensive judgment of investigator, a subject had an infection of the implant site, when the shunt was implanted, such as ventriculitis, meningitis, peritonitis, and local implant skin infection;
4. A subject was simultaneously implanted another shunt system excluding Bactiseal Catheter;
5. A subject had a contraindication of the shunt operation;
6. A subject had uncorrected coagulopathy or any bleeding disorder.

7 Research Process

The research process included: Screening and enrollment of subjects, Days -30 to -1 before the operation, Day 0, the day of operation, and one-year follow-up (Days 1-365) after the operation.

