7.4 Postoperative follow-up period: Days 1-365

An adverse event (except an anticipated adverse event) discovered during the review of postoperative history or hospital database (if any) should be recorded:

The time, description, concomitant therapy, and outcome of an adverse event, information related to the operation and the product, if the implanted part was taken out due to an adverse event, and concomitant medication and treatment should be recorded.

Additional records were required for the following special adverse events:

1. Infection: Infection site which is usually classified into intracranial, skin, and abdominal infections. For intracranial infection, time of infection, white blood cell count, red blood cell count, neutrophilic granulocyte count, hemoglobin content, alanine aminotransferase (ALT), aspartate aminotransferase (AST), C-reactive protein, blood glucose, traits and color of CSF, cell count, Pan's test results, contents of protein, sugar, and chloride in CSF, bacterial culture type, and bacterial susceptibility to rifampicin and clindamycin should be recorded. For skin infection and abdominal infection: white blood cell count, red blood cell count, neutrophilic granulocyte count, bacterial culture type, and bacterial susceptibility to rifampicin and clindamycin should be recorded.

2. Obstruction of catheter: site, reason (judged by an investigator), and nature of obstruction should be recorded.

3. Leakage of CSF: time and position of leakage should be recorded.

4. Mechanical failure: type of mechanical failure should be recorded, including falling out, displacement, twisting, and rupture.

A patient who died within one year was still considered as a complete case. The form of SAE should be completed. And the death should be specified in this study endpoint table.

8 Adverse Event Reporting

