8.4 Duration of follow-up after an adverse event

As this is a retrospective study, it did not intervene in subjects' normal treatment. Therefore, all adverse events were properly dealt with by an investigator based on medical requirements. And no additional

Proposal No.: C-BSEAL-001
Date of proposal: V1.0/2019-11-18
follow-up would be performed.

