9.1 Reason of early termination

Possible reasons of early termination include, but are not limited to, the following:

- Withdrawal of informed consent: (For a research center which required its subjects to sign the ICF) a subject decided to withdraw from this study. The decision must be "determined by the subject himself/herself" and recorded in the subject's research file;
- Early termination of this study: The sponsor might decide to suspend this study in advance for any reason.

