10.3 Sample size

This study would provide the non-infection rate of Bactiseal Catheter within one year and assure the acceptable threshold of 95% confidence interval (CI). If the sample size was N_0 at first, the uninfected patients t year later would approximately be:

$$N(t) = N_0 e^{-(r1+r2)t}$$

r1 and r2 represent the infection rate and the dropout rate.

The parameters of K-M survival analysis (e.g., non-infection rate) were estimated according to Peto. The two-sided confidence interval threshold of 95% of K-M survival t years after the operation was defined as S(t) in accordance with the following formula:

$$margin = 1.96 \sqrt{[S(t)]^2[1 - S(t)]/N(t)}.$$

According to a literature review, the annual infection rate of a catheter with antibiotics was 3.2% (95% CI 1.3-4.4%). By taking into account the differences among centers and of operating standards, the lower limit of 95% confidence interval of the infection rate was considered as the anticipated infection rate. The annual infection rate of a catheter with antibiotics was 4.3%. Therefore, the non-infection rate was 95.7% within one year. If 150 (100 subjects historical data from DPS-201501 study with additional 50 new subjects enrollment) subjects and the dropout rate was 10%, according to the first formula, the sample size of infected subjects one year after the operation, N(1), would be:

$$N(1) = N_0 e^{-(r1+r2)} = 150 * e^{-(0.044+0.1)} = 130.$$

The threshold of 95% CI of non-infection rate within one year would be:

$$margin = 1.96 \sqrt{[95.7\%]^2[1 - 95.7\%]/130} = 3.4\%.$$

The precision of 3.4% is considered acceptable for this study.

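### Eligibility asks for one year of elapsed time, not of documented observation, and no last-contact or censoring date is set: short charts count as event-free in the crude adverse-event percentages and may count as infection-free to Day 365

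*Combined protocol and SAP*

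**What the plan says.** Inclusion criterion 3 in section 6.2 reads "A subject received hydrocephalus shunt at least one year ago". No inclusion or exclusion criterion requires records or contact after surgery.

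Section 7 sets the window as "one-year follow-up (Days 1-365) after the operation". Section 7.4 fills that window from existing sources: an event "discovered during the review of postoperative history or hospital database (if any) should be recorded". It then lists what to record when an event is found. It asks for nothing about a patient with no event, including when that patient was last seen. Section 8.4, which deals with follow-up after an adverse event, says "As this is a retrospective study, it did not intervene in subjects' normal treatment" and that no additional "follow-up would be performed".

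Section 10.3 allows for loss: "r1 and r2 represent the infection rate and the dropout rate", with dropout set at 10%. It does not say what dropout means in a chart review. Section 10.6 defines the per-protocol population by the eligibility criteria alone. It plans Kaplan-Meier with a Peto interval for infection, and frequencies and percentages for categorical data. It gives no censoring rule, and no time-to-event or person-time method for adverse events.

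**The concern.** The study's purpose is safety over one year, and section 10.7 says the report will support extension of the product registration. When outcomes are read from charts, a blank page can mean that nothing happened or that nobody was looking. Without a last-contact date the two cannot be told apart.

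For adverse events, the planned percentages treat both as no event. For infection, the analyst has no specified date on which to censor. If a silent chart is carried to Day 365, events treated elsewhere are lost and unobserved time stays in the risk set. Both errors make the device look safer: rates are too low and the interval is too narrow. The Peto margin also needs the number still at risk at one year, which cannot be known without last-contact dates.

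**Working it through.** **Inputs from section 10.3.** N0 = 150 (100 from DPS-201501 and 50 new); anticipated one-year infection rate 4.3%, so S = 0.957; dropout 0.1; stated N(1) = 130 and margin 3.4%.

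**Assumptions not in the documents.** A share f of charts stops at Day 14; the hazard is constant; infections after a chart stops are not captured.

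**1. The plan's own figures.** N(1) = 150 × exp(−(0.044 + 0.1)) = 129.9. Margin = 1.96 × 0.957 × √(0.043/129.9) = 3.41 points. Using 0.043, the rate in the text, gives N(1) = 130.0 and the same margin. The stated 130 and 3.4% reproduce, and they already allow for 10% loss.

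**2. Short charts counted as infection-free to Day 365.** h = −ln(0.957) = 0.04395. Risk by Day 14 = 1 − exp(−0.04395 × 14/365) = 0.168%. Observed rate = (1 − f) × 4.3% + f × 0.168%.

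| Who is affected | f = 10% | f = 30% |
|---|---|---|
| All 150 subjects | 3.89% | 3.06% |
| Only the 50 new subjects (effective f is one third) | 4.16% | 3.89% |

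**3. Sensitivity to timing (all 150 affected).** For charts ending at Day 7 or Day 30, f = 30% gives 3.04% or 3.12%. If half of the year's infections occur before the chart stops, the observed rate is (1 − f) × 4.3% + f × 2.15%: 4.09% at f = 10% and 3.66% at f = 30%.

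**4. Same charts censored at last contact.** If censoring is non-informative, the Kaplan-Meier estimate stays at 4.3%. N(1) = 150 × 0.957 × (1 − f), and the margin is 1.96 × 0.957 × √(0.043/N(1)).

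- f = 10%: N(1) = 129.2, margin 3.42 points.
- f = 30%: N(1) = 100.5, margin 3.88 points.

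For contrast, carrying the f = 30% charts to Day 365 gives S = 0.9694 and N(1) = 150 × 0.9694 = 145.4. The margin is then 1.96 × 0.9694 × √(0.0306/145.4) = 2.76 points: a narrower interval around a rate that is too low.

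**5. Adverse events.** The dilution in step 2 applies to any crude percentage over all eligible subjects. The plan gives no anticipated adverse-event rate, so I put no number on it.

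**The case against.** A reader might infer that the plan tells sites to close silent charts as infection-free at Day 365. It does not. No section says so, and two features point towards censoring: Kaplan-Meier is the chosen method, and N(1) allows for 10% dropout. Section 7.4 calls a patient who died within the year a complete case, which suggests that incomplete cases are foreseen.

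A reader might also infer that section 9.1 leaves no exit for a patient lost to contact. It names "Withdrawal of informed consent: (For a research center which required its subjects to sign the ICF) a subject decided to withdraw from this study" and termination by the sponsor, but introduces them as an open list. Loss of contact is not excluded as an exit reason.

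Other safeguards exist. The data collection table has an end-of-study/exit entry in the postoperative column. Section 11.3.1 requires follow-up information and the subject's condition at completion or withdrawal to be kept as source documents. Section 11.3.2 requires endpoints to be verified for every subject. The case record form is not among the documents, so it may hold an exit date.

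On size, no document supports any particular share of short charts. The follow-up rules for the 100 DPS-201501 subjects cannot be seen. The analysis is descriptive, with no pass/fail criterion (sections 10.2 and 10.4).

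All of this stands against the stronger readings. It does not supply what is missing. Naming Kaplan-Meier does not fix a censoring date, an exit entry is not tied to last contact, and verifying recorded endpoints cannot reveal an event the chart never held. None of it touches the adverse-event denominators.

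**Conclusion.** The point holds as an under-specified collection and analysis rule whose likely error runs in one direction. For adverse events it follows from the plan as written: a chart that ends at discharge stays in the crude denominator as event-free. For infection, carrying such a chart to Day 365 is possible but not prescribed.

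Under the stated assumptions, a true 4.3% would appear as 3.9% (f = 10%) or 3.1% (f = 30%) if all 150 subjects are affected, and as 4.2% or 3.9% if only the 50 new subjects are. Early clustering of infections reduces the bias. The stated 3.4% margin survives 10% censoring and rises to about 3.9% at 30%.

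This merits correction before data extraction is completed, because an analyst cannot repair it later without a date that the plan does not ask for. It does not invalidate the design.

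**What to change.** - **Section 7.4 and the end-of-study/exit form:** for every subject, record the date of the last documented clinical contact on or before Day 365 (visit, admission, imaging or recorded call). Obtain the same date for the DPS-201501 subjects where available. Add last contact before Day 365 as an exit category, and use it to define dropout in section 10.3.
- **Section 10.6, infection:** censor subjects without infection at that date, and report the number and percentage observed to Day 365.
- **Section 10.6, adverse events:** beside the crude percentage, give a time-to-event estimate or a percentage with a follow-up-complete denominator.
- **Section 6.2:** leave inclusion criterion 3 as it is, so that patients with short charts are censored and not excluded.

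**Cost.** One chart-derived date per subject and a few sentences in section 10.6. Retrieving the date for the historical subjects may take extra work or prove impossible for some. The interval may widen slightly. Last-contact censoring can also be informative: ill patients return more often than well ones, which would push the infection estimate upward, and a follow-up-complete denominator has the same weakness. For that reason, show the estimate with all subjects followed to Day 365 as a sensitivity analysis.
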